Overview: Design and Methods. This three-year development project consists of 3 stages. **Stage one** (months 1-6) involves establishing a Development Team (DT) that will review the initial draft of TAPES and provide feedback to ensure that TAPES is acceptable to teachers and feasible for the school setting. **Stage two** (months 7-20) involves two successive open trials of the TAPES protocol with 15 teachers and 20 children. This stage will allow for "trial runs" of the training to assess feasibility, acceptability and utility of the training. Data and qualitative feedback gleaned during the first open trial will inform modifications for the second open trial. We will present and discuss data with the DT after each open trial. We will also ask 5 teachers from open trial 1 to test out the revisions for open trial 2. Based on knowledge gained in this stage, appropriate modifications will be made for stage three. **Stage three** (months 21-34) involves a pilot RCT using a randomized controlled design comparing TAPES to the Teacher Anxiety Training (TAT). TAT (developed by the PIs for use in other studies and described below) will be used to represent "typical" teacher professional development training. The RCT will be conducted in three phases. Phase 1 consists of recruiting, randomizing, and training

teachers in either TAPES or TAT. Also during this phase (but after the training), teachers will recruit anxious children and study staff will screen and evaluate them to determine eligibility. In Phase 2 teachers will implement TAPES or TAT. Phase 3 involves a post-intervention (after 8 weeks) and a three-month follow-up assessment of the primary (teacher behavior) and secondary (child) outcomes. Trained independent evaluators (IEs) will assess primary outcomes (teacher behavior). The culmination of these iterative stages will be a final version of the training that will be ready for evaluation in a larger efficacy trial.

DETAILED DESCRIPTION OF EACH STAGE

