
Phase 1 - Recruitment, Randomization, Training, Student Screening, and Baseline

Evaluations: In Phase 1, teachers will be randomly selected from the pool of interested participants and randomized to TAPES or TAT. Once randomized, teachers will complete their assigned training. Teachers will then identify potentially eligible students from their classes and provide information about the study to their parents. Interested parents will contact study staff and complete a brief phone screen. Students who appear eligible based on the phone screen (e.g.,

have elevated anxiety; are in elementary school) will be invited to complete informed consent and a full baseline evaluation with an IE (see Table 1 for measures). Families who "pass" the baseline evaluation (i.e., student obtains a *t* score of 60 on Spence Children's Anxiety Scale (SCAS) and/or a CSR of at least 3 on the ADIS-V) will be considered eligible (see Inclusion/Exclusion criteria below).

Phase 2 – TAPES/TAT Implementation: Teachers will implement TAPES or TAT depending on their random assignment over 8 weeks from child enrollment.

Phase 3 - Post- and Follow-up Evaluations: At the end of the 8 weeks, teachers and children in both groups will complete a post evaluation (see Table of Measures). Teachers, students, and parents will complete a TAPES satisfaction measure and provide feedback to enhance the protocol. Teachers will complete an exit interview. Students who need mental health services will be referred to the school counselor or community provider for treatment. A 3 month follow-up evaluation to assess sustained use of TAPES/TAT skills will be conducted.

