- School Attendance, Discipline, and Parent's Missed Work – This questionnaire will obtain information from parents about their children's school attendance, disciplinary actions taken against their child and the amount of work that they have missed due to anxiety related reasons. This will be completed at baseline and all follow up assessments.

- *Child Health Utility Index (CHUD)* – This 9-item questionnaires assess the student's overall health and functioning in various domains. It is commonly used in the context of intervention cost-effectiveness research and demonstrates adequate psychometric properties (Furber & Segal, 2015).

Instrument	Purpose	Rater	Time	Completion
			Point	time
Primary Outcomes: Teacher Knowledge and Skills				
Teacher	Assess teacher knowledge of anxiety	Teacher	BL, PO	10 min
Knowledge	reduction strategies			
Assessment				

Table 1 Assessment of Study Measures

Classroom	Assess accurate use of skills by	IE,	BL, PO,	30 min
Observations of	teacher in classroom	Teacher	FU	
Teachers Skills				
Usability Measu	res			
Teacher	Assess teacher ability to learn new	Teacher	BL, PO	10 min
Knowledge	information			
Assessment				
Classroom	Assess whether teachers can use	IE	Pre-	30 min
Observation of	skills		Training	
Teachers Skills			, BL,	
			PO, FU	
Teacher and	Assess teacher ability to identity	IE	WKLY	5 min
Child	anxious youth			
Recruitment				
Iracker		TT 1		- ·
Teacher Time	Assess number and length of school-	Teacher	WKLY	5 min
Log	nome meetings and other			
	interactions with the study child			
Eassibility Maas				
Training Meas	Assass togeher training satisfaction	Tanahar	Doct	5 min
Satisfaction and	as marker of willingness to use the	reacher	r USI training	5 11111
Feedback	TAPES or TAT intervention or		uannig	
nuestionnaires	skills			
TAPES	Assess perceptions of feasibility	Teacher/	PO	5 min
Satisfaction and	satisfaction and helpfulness of	Parent/	10	5 11111
Feedback	intervention	Child		
Ouestionnaires				
Satisfaction	Assess parent and teacher	Teacher/	WKLY	5 min
Forms, Meeting	satisfaction and perceptions of	Parent		
1-5	helpfulness of each meeting			
 		 	*****	- ·
Satisfaction	Assess child satisfaction and	Child	WKLY	5 min
Forms, Meeting	perceptions of helpfulness of each			
2-5	meeting			
Exit Interview	Document teachers experience in	Ы	РО	20 min
	program: perceived barriers, etc.		10	
Teacher and	Assess interest and ability to	IE	WKLY	5 min
Child Retention	implement intervention within			

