burnout, teacher efficacy; teacher behavior) and child characteristics (e.g., gender, age, baseline anxiety symptoms, classroom functioning). To test the main hypothesis, that teachers in TAPES, compared to TAT, will have higher knowledge about anxiety reduction, we will examine scores on the *Teacher Knowledge Assessment* at post-training, and at the end of school year as outcomes in GLM controlling for teacher pre-training score. Let y_i denote the post-training or end of school year test score of teacher i, x_{i1} and x_{i2} denote teacher i's group assignment and pre-training test score, respectively, and ε_i denote resident term. Rejecting $\beta_1 \leq 0$ and $\beta_3 \leq 0$ in the model: $y_i = \beta_0 + \beta_1 \times x_{i1} + \beta_2 \times x_{i2} + \beta_3 \times x_{i1} \times x_{i2} + \varepsilon_i$ suggests that TAPES teachers' post-training test scores are higher and they have a greater gain in knowledge than TAT teachers. Teacher-specific covariates can be added to the above model as needed. To test the hypothesis that TAPES, compared to TAT, will result in greater use of anxiety reduction skills in the classroom, IE's Classroom Observation of Teachers Skills rating for each pair of teacher and anxious student at baseline, post-intervention, and 3-month follow-up will be modeled in GLMM. Now rating, y_{ijk} are nested within teacher k and student j, who is nested within teacher k, in the multilevel equations: Level 1: $y_{ijk} = \pi_{0jk} + \pi_{1jk} \times \text{timepoint}_{ijk} + e_{ijk}$; Level 2: $\pi_{0jk} = \beta_{00k} + r_{0jk}$ and $\pi_{1jk} = \beta_{10k} + r_{1jk}$; Level 3: $\beta_{00k} = \gamma_{000} + \gamma_{001} \times w_k + u_{00k}$ and $\beta_{10k} = \gamma_{100} + \gamma_{101} \times w_k + u_{10k}$; where w_k denotes teacher k's intervention-training group assignment with e, r, and u representing error terms in the respective levels. Teacher-specific (e.g., years of teaching experience, teaching efficacy) and child-specific (e.g., age, baseline anxiety severity) covariates can be added to Levels 2 and 3 equations as needed. Aim #4 (Secondary Outcomes): To examine the impact of TAPES relative to TAT on student outcomes. Change scores on student mental health (e.g., Spence Children's Anxiety Scale, SCAS) and academic achievement (e.g., Woodcock-Johnson Tests of Achievement) from pre-to postintervention and 3-month follow-up will be modeled as GLMM similar to above in Aim 3. **Exploratory aims**: To examine mediators (proposed in the theory of change, see Figure 1 in Appendix) and predictors and moderators (e.g. Teacher Background Form, MBI-Educators Scale) of TAPES impact on teacher knowledge and behavior. Structural equation modeling (SEM) will be used to explore potential predictors (e.g., baseline teacher burnout as measured by MBI-ES), mediators (e.g., subscale scores from the OSTES) and moderators (e.g., years of teacher experience) on teacher behavior change (e.g., change score on the Classroom Observation of Teachers Skills at pre-, post-intervention and 3-month follow-up). Sub study: Aim #1: Assess the direct and indirect cost of pediatric anxiety among youth enrolled in the TAPES intervention. This aim involves the modification of existing measures of direct and indirect cost. These measures will be administered to parents and teachers at existing TAPES assessment time points (i.e. baseline, post intervention and three-month follow up). Aim #1a: Estimating the cost of pediatric anxiety through direct and indirect costs. Aim #2: To examine the child and parent benefit of TAPES compared to UC. This aim involves estimating the cost of TAPES relative to the UC condition in relation to direct and indirect costs. Exploratory Aim: To examine family demographic factors as moderators of pediatric anxiety cost. **Power Analysis.** Although this is a development study proposing a small pilot RCT, attempts were made to estimate statistical power for the key outcomes based on existing literatures on similar measures (see White et al., 2011 for Teacher Knowledge Assessment and Barrett et al., 2005 for child anxiety using the SCAS). Using Optimal Design version 3.0 calculations for both variables were based on an anticipated enrollment of 20 teachers in each group (and 1-2 students per teacher). We assumed a conservative within-teacher ICC of 0.10 (Eldridge et al., 2004) and

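### Table 1 schedules two administrations of the primary knowledge test, Aim 3 needs three, and BL is not defined for teacher-level measures

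*Combined protocol and SAP*

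**What the plan says.** **Analysis.** Data Analytic Plan, Aim #3, takes knowledge scores "at post-training, and at the end of school year as outcomes in GLM controlling for teacher pre-training score". The model notation lets the response "denote the post-training or end of school year test score of teacher i", and the second regressor is that teacher's pre-training score. The model also contains a group-by-pre-score interaction.

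**Schedule.** The first line of the primary-outcome row in Table 1 reads "Assess teacher knowledge of anxiety Teacher BL, PO 10 min". The usability row for the same test also gives BL and PO. Neither row has a pre-training, post-training, follow-up or end-of-year entry.

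**Sequence.** Stage 3, Phase 1 says "Once randomized, teachers will complete their assigned training. Teachers will then identify potentially eligible students from their classes", with the phone screen and baseline evaluation after that. The Research Plan overview says "Also during this phase (but after the training), teachers will recruit anxious children and study staff will screen and evaluate them to determine eligibility". Phase 3 places the post evaluation at the end of the 8 implementation weeks.

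**The concern.** Field staff work from the schedule and the analyst works from Aim 3, and for a primary outcome the two do not match. Staff who follow Table 1 will hold two scores per teacher where the analysis expects three. A missed pre-training score cannot be recovered once the teacher has been trained, and the claim of a greater gain in knowledge depends on it.

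A second, conditional risk follows. If BL is taken after training and then stands in for the missing covariate, the model adjusts for a variable that training has already changed, and part of the effect under test is removed.

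**Working it through.** **1. The plan's own figure.** The Power Analysis section gives 80% power for d = 1.19 with 20 teachers per group and alpha 0.05. It does not state sidedness.
- Two-sided, normal approximation: 1.19 × √(20/2) − 1.960 = 3.763 − 1.960 = 1.803, so power is 96.4% (95.6% by noncentral t). One-sided, it is 98.3%.
- Smallest effect detectable with 80% power, two-sided: (1.960 + 0.842) × √(2/20) = 0.89 (0.91 by t).

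The 80% is not reproduced and is true only as at least 80%. This is a separate, conservative discrepancy, and the point here does not rest on it.

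**2. Counting scores.** Needed: pre-training (covariate), post-training (outcome) and end of school year (outcome), so 3. Scheduled: BL and PO, so 2.
- If BL is before training, the covariate exists. PO can supply at most one of the two outcomes.
- If BL is after training, it might serve as the post-training outcome, but the covariate is missing. If BL is used as the covariate instead, PO is the only outcome score left.

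PO cannot be assumed to be the end of the year. Procedures for Summer Months requires only that at least 10 school weeks remain at enrolment, so PO may fall well before the year ends.

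**3. What BL means for a teacher measure.**

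| Suggests BL follows training | Suggests BL precedes training |
|---|---|
| Stage 3, Phase 1 and the overview place student identification and evaluation after training | The Measures section says the test is meant to gauge what teachers already know as well as the effect of training |
| The usability row for Classroom Observation in Table 1 lists Pre-Training separately from BL | The theory of teacher behaviour change calls self-efficacy and burnout pre-training factors; Table 1 first measures both at BL |
| Teacher payment for baseline, post and follow-up measures is per student | That payment covers measures on each student, whereas the knowledge test is scored once per teacher |

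The other two Table 1 rows for Classroom Observation omit the Pre-Training label, so the table does not use it consistently. The protocol does not settle the question.

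**4. Size of the conditional harm.** The inputs are d = 1.19 at the outcome (Power Analysis), 20 per arm, two-sided 0.05, equal unit SDs and no interaction term. Two inputs are assumed because the protocol does not give them: the within-group correlation r between BL and outcome, and the between-arm effect already present at BL.

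Adjusted effect = d at outcome − r × d at BL.
- BL before training: 1.19 − r × 0 = 1.19 for every r.
- BL carries the full effect: 1.19 − 0.3 × 1.19 = 0.83; 1.19 − 0.5 × 1.19 = 0.60; 1.19 − 0.7 × 1.19 = 0.36.
- BL carries about half (0.6): 1.19 − 0.3 × 0.6 = 1.01; 1.19 − 0.5 × 0.6 = 0.89; 1.19 − 0.7 × 0.6 = 0.77.

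Power by simulation (20,000 trials per setting):

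| Covariate | r = 0.3 | r = 0.5 | r = 0.7 |
|---|---|---|---|
| True pre-training score | 96.5% | 98.8% | 99.9% |
| BL with about half the effect | 86.7% | 84.6% | 87.5% |
| BL with the full effect | 62.4% | 42.7% | 25.7% |

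**The case against.** A reader might infer that BL is established as a post-training time point, so that the planned analysis is certain to be biased. The documents do not support that. The baseline evaluation that follows training in Phase 1 is the child's eligibility evaluation. It does not date the teacher test, whose stated purpose needs a score before training. Aim 3 also names the pre-training score as the covariate, so using BL after training in its place would be a further decision that no section of the plan makes.

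The figures deserve caution too. Full effect at BL is the severe case; with about half, power stays above the planned 80%. The Power Analysis describes its effect sizes as within-group changes, so 1.19 is not clearly a TAPES-versus-TAT difference. TAT also teaches about anxiety and effective interventions, so both arms may gain. The formula leaves out the interaction that Aim 3 includes.

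Finally, the Measures section says that the battery will be revised after development-team and open-trial feedback, so Table 1 is provisional.

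All of this stands against a categorical claim about BL and against a single figure for the bias. It does not remove the mismatch in the count. That the table is provisional is a reason to correct it before the RCT, since no text says this entry will change.

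**Conclusion.** The point holds as an internal inconsistency in a primary analysis: three scores are needed and two are scheduled, so at least one is missing however BL and PO are read. That conclusion rests on no assumption.

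The covariate problem is conditional. It arises only if BL follows training and is also used as the covariate. Its size then depends on an assumed correlation and an assumed effect at BL, and ranges from no loss to a substantial one. It should be reported as a risk created by the undefined label, not as a demonstrated bias.

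**What to change.** - In both Table 1 rows for the Teacher Knowledge Assessment, and for both arms, list Pre-Training (before the training session, preferably before randomisation), Post-Training and End of School Year.
- State whether the administration at PO, after the 8 weeks, is kept as an additional test or is one of these three.
- State in Aim 3 that the GLM covariate is the score collected before training.
- Define BL for teacher-level measures relative to the training day.

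Amending Aim 3 to match the scheduled times would also restore consistency. It would drop a stated primary time point, and the covariate would still have to be fixed as a score taken before training.

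The cost is a table correction and about one extra 10-minute test per teacher, which Aim 3 already assumes: 40 × 10 = 400 minutes across the 40 RCT teachers. The sample size does not change. The correction should be in place before the first RCT teacher is trained.

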-Teacher Knowledge Assessment is a 26-item short answer and multiple choice test of anxiety reduction strategies to gauge teachers' prior knowledge and the effectiveness of training. This measure was adapted from an existing knowledge assessment test for school clinicians, which showed an increase in knowledge pre to post-training ([name] et al., 2008).

-*Classroom Observation of Teachers Skills* is a form completed during direct observations of the teacher during normal class activities (e.g., math or reading). The observations are coded by tallying the frequency of specific behaviors that have a positive or negative impact on student anxiety. Using a 5 point Likert scale, observers provide an overall rating of teacher's behavior in both domains.

Usability Measures- The following measures assess whether teachers can understand and learn how to use the skills and whether they can implement the skills effectively and efficiently.

- Teacher Knowledge Assessment (above) will assess ability to learn skills.

- *Classroom Observation of Teachers Skills* (above) will assess use of skills in the classroom. -*Teacher and Child Recruitment Tracker* will be used to record recruitment of teachers/children as well as obstacles to recruitment. Obstacles will be addressed in team meetings and with DT. -*Teacher Time Log* is a form completed by teachers to log the amount of time spent using TAPES/TAT skills with each study student.

Feasibility Measures – The following measures assess whether the training skills can be implemented within an authentic school setting.

-Training Satisfaction and Feedback Questionnaire ([name] et al., 2008, 2011) is a 16-item measure completed anonymously by teachers who rate the helpfulness of training content and format (e.g., role play, videos), overall satisfaction and perceived helpfulness of TAPES/TAT skills for students with anxiety, and their preparedness to conduct conjoint meetings using a 4-point Likert-type scale (1 = not at all helpful to 4 = very helpful). Open-ended questions ask about the most/least helpful aspects of training and suggestions for improvement.

- *TAPES & TAT Satisfaction and Feedback Questionnaires* ([name] et al., 2012) will be adapted for this study from an existing questionnaire and will assess satisfaction and helpfulness of skills used with anxious and in the classroom.

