
an alpha level was set at .05. Below is a list of minimum effect sizes (calculated as within-group difference in change score, divided by the pooled standard deviation) needed to be detectable with 80% power. With 20 teachers in each group, we will have 80% power to detect the effect size found by White et al. (2011) of d = 1.19 on teacher knowledge. With 30 students in each group, we will have 80% power to detect the effect size found by Barret et al. (2005) of d = .92on child anxiety (effect sizes based on moderately anxious students at pre-post timepoints). Time Table : We are requesting funds for three years. The first six months will be for administrative study start-up tasks (hiring, IRB approval), IE training, and TAPES refinement and review of materials with DT (Stage 1). Months 7 - 20 (Stage 2) will be devoted to recruitment of teachers and students for open trials and further adaptation and refinement of TAPES. Months 21 to 34 will be devoted to implementing the RCT. The final two months (35-36) will be devoted to completing data analyses and manuscript preparation. Personnel: Relevant Expertise of Research Team. The core UCHC research team (Drs. [name] & [name]) along with our consultants have over 20 years of experience in conducting research on the development, evaluation, and dissemination of school-based programs for teachers and school personnel. In addition, the team has extensive experience providing education and training in anxiety reduction skills to school-based and community personnel. Both [name] & [name] moved to UCHC in 2014. In that time they have successfully partnered with 7 CT school districts which now serve as authentic environments for their funded research. They have trained over 40 school clinicians and 17 school nurses as part of their research-exceeding initial recruitment goals. Together they also established the Child/Adolescent Anxiety and Mood Program (CAMP). CAMP conducts community-based research focusing on child and adolescent anxiety and mood disorders, with an emphasis on intervention and dissemination. CAMP now has research coordinators, postdoctoral fellows, and research assistants who work together to recruit research participants and implement studies funded by NIMH and IES. CAMP holds weekly and monthly research meetings that are attended by residents, fellows, and faculty. Currently, CAMP members include 2 faculty, 3 postdocs, 2 Masters level staff, and 8 student research assistants. Finally, Drs. [name] and [name] share responsibility for teaching seminars on child anxiety for psychiatry residents at UCHC. Together, they have given numerous seminars and presentations on childhood anxiety and CBT to a variety of audiences (e.g., parents, teachers, counselors, physicians, and psychiatrists) and have trained school-based clinicians and nurses in the principles and strategies of delivering CBT to anxious youth within schools. These prior experiences have prepared the investigative team to successfully conduct this proposed study. This project reflects a significant and logical next step in this program of research by training teachers in the identification and support of anxious youth. Below is a list of key personnel that will also support this grant, their qualifications, roles, responsibilities, and percent of time and calendar months per year to be devoted to the project are listed below. Evidence of publishing in peer-reviewed scientific journals is documented in the biosketches. Each team member has experience that will ensure the successful implementation of this study.

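### The primary knowledge rule tests the group difference at a pretest of zero and a group-by-pretest interaction, not the average training effect; under a uniform benefit the interaction test succeeds only about 5% of the time

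*Combined protocol and SAP*

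**What the plan says.** Aim #3 of the Data Analytic Plan states as its main hypothesis "that teachers in TAPES, compared to TAT, will have higher knowledge about anxiety reduction". Knowledge scores at post-training and at the end of the school year are to be analysed "as outcomes in GLM controlling for teacher pre-training score". The model is y = β0 + β1·x1 + β2·x2 + β3·x1·x2 + ε, where "x_{i1} and x_{i2} denote teacher i's group assignment and pre-training test score, respectively". No centring of the pretest is stated.

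The decision rule is "Rejecting $\beta_1 \leq 0$ and $\beta_3 \leq 0$ in the model", which "suggests that TAPES teachers' post-training test scores are higher and they have a greater gain in knowledge than TAT teachers". The sentence does not say whether both rejections are needed for one joint conclusion or whether each coefficient supports its own.

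The Power Analysis section says "With 20 teachers in each group, we will have 80% power to detect the effect size" of d = 1.19 on teacher knowledge, and that "an alpha level was set at .05". It does not mention an interaction. The outcome "is a 26-item short answer and multiple choice test of anxiety reduction strategies"; no scoring, pretest mean, SD or pre-post correlation is given.

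**The concern.** The hypothesis concerns an average difference between arms. Neither coefficient in the rule is that average once the interaction is in the model and the pretest is uncentred.

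- **β1** is the group difference at a pretest score of zero, which may lie outside the observed scores.
- **β3** says whether the training effect is larger for teachers who already knew more. A training that helps everyone equally has β3 = 0. One that helps the least informed teachers most has β3 < 0, so the plan would withhold its greater-gain conclusion in a case that a training programme might well hope for.

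Knowledge is one of two primary outcomes. Followed literally, the rule could miss a large true benefit. If β1 is read alone, it could also report a benefit where the average effect is zero.

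**Working it through.** **1. What the coefficients mean.** At pretest x the TAPES–TAT difference is β1 + β3·x, so the average effect is β1 + β3·(mean pretest). Now take gain, g = y − x2, as the outcome: g = β0 + β1·x1 + (β2 − 1)·x2 + β3·x1·x2 + ε. Only the pretest slope changes; β1 and β3 are the same. With the pretest adjusted for, the average difference in gain is therefore the same number as the average difference in post score, and β3 is no more a measure of gain than it is of level.

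**2. The plan's own power figure.** Inputs from the Power Analysis section: 20 per arm, d = 1.19, alpha .05. Noncentrality = 1.19 × √(20/2) = 3.76.

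- Two-sided power = Φ(3.76 − 1.96) = 96.4% (95.6% with the t distribution).
- One-sided power = Φ(3.76 − 1.645) = 98.3% (98.0% with t).
- Exactly 80% at d = 1.19 needs about 12 per arm two-sided. With 20 per arm, the smallest d detectable with 80% power is about 0.89–0.91.

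The stated 80% therefore holds only as a lower bound. It is power for an average difference and does not describe the β1/β3 rule.

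**3. β3 under a uniform benefit.** The true β3 is 0, so rejecting β3 ≤ 0 is a false positive with probability alpha: 5% one-sided, or about 2.5% in the positive direction of a two-sided .05 test. No assumption about the pretest or d is needed.

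**4. Precision of the uncentred β1.** In large samples, SE(β1, raw) / SE(group effect without interaction) ≈ √(1 + (mean/SD)²).

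- mean/SD = 2: √5 = 2.2.
- mean/SD = 13/3 = 4.33: √19.8 = 4.4.

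Simulation with 20 per arm gave 2.3 to 4.7 over assumed means of 10–13 and SDs of 3–5. The β1 and β3 estimates correlate at −0.90 to −0.98 there, so both are seldom significantly positive in the same trial.

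**5. Simulation.** Least squares, 20 per arm, 20,000 trials per setting, normal pretest, outcome SD equal to pretest SD, uniform benefit d = 1.19 taken as between arms, one-sided .05. Pretest mean, SD and pre-post correlation r are assumptions. Rejection rates at r = 0.5:

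| Pretest mean / SD | β1 (raw) | β3 | Both | Group effect, no interaction |
|---|---|---|---|---|
| 13 / 3 | 22.9% | 5.0% | 0.0% | 99.4% |
| 10 / 5 | 56.8% | 5.3% | 0.07% | 99.5% |
| 5 / 5 | 88.4% | 5.1% | 2.4% | 99.5% |

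Over r = 0.3–0.7, β3 stays at 4.7–5.3%. At means 10–13, β1 runs from 20% to 71% and both are rejected in at most 0.3%. At 5/5, β1 runs from 83% to 96% and both from 1.8% to 3.5%. The group effect without the interaction is rejected in 98–100% throughout. With the pretest centred, β1 is rejected in 98.1%, 99.3% and 100% at r = 0.3, 0.5 and 0.7, and its SE is 1.01 times that of the model without the interaction.

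**6. Non-uniform benefit (r = 0.5).**

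- Average d = 1.19, low scorers gaining more (β3 = −0.2 to −0.3): β3 is rejected in 0.4–1.1%.
- Average d = 1.19, high scorers gaining more (β3 = +0.2 to +0.3): both are rejected in at most 0.2% at means 10–13, and in 7–11% at 5/5.
- Average d = 1.19, β3 = +0.3, mean/SD = 4: in SD units the true β1 is 1.19 − 0.3 × 4 ≈ 0, and β1 is rejected 5% of the time.
- Zero average effect, β3 = −0.5, mean/SD = 4: the true β1 is 0.5 × 4 = 2.0 SD, and β1 ≤ 0 is rejected in 50% of trials, against about 5% for the model without the interaction.

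**The case against.** The sentence may intend two separate conclusions, and it says only that the rejections suggest them; no go/no-go decision in this pilot hangs on it. The hypothesis, worded as controlling for the pretest, already points to the usual adjusted comparison. Under a uniform benefit the true β1 equals the average effect. The d of 1.19 is defined in terms of change scores in unclear wording, and TAT is itself an active training, so the real contrast may be smaller. The pretest values are invented, and a normal pretest with mean 5 and SD 5 puts about 16% of teachers below zero.

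Much of this stands as qualification:

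- Under a uniform benefit the harm to β1 is lost precision; β1 becomes the wrong quantity only when β3 differs from zero.
- The false signal from β1 at zero average effect arises only if β1 is read alone, because β3 is then negative and the joint rule almost never fires.
- The 5/5 row is an unlikely extreme and little weight should be put on it.
- The 98–100% depends on d. With mean 10/SD 4 and r = 0.3–0.7, the adjusted comparison has 82–96% power at d = 0.8, 61–82% at 0.6 and 36–53% at 0.4.

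None of it rescues the rule. The greater-gain conclusion fails on the separate and the joint reading alike, and its 5% ceiling does not depend on d or on the pretest. Nor can centring be presumed: the Aim #1 model writes its covariate centred and has no interaction, whereas the Aim #3 model is not centred and has one. Centring would repair β1 but not the meaning given to β3.

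**Conclusion.** The concern holds. As written, the primary knowledge rule does not test the hypothesis it states. The firm part follows from the model alone: β3 is effect modification, and under a uniform benefit it is rejected at alpha, about 5% one-sided, whatever the size of the training effect.

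The size of the remaining damage depends on assumptions. With a between-arm d of 1.19, r of 0.3–0.7, and pretest means of 10–13 with SDs of 3–5, the uncentred β1 has 20–71% power and the joint rule at most 0.3%, where the ordinary adjusted comparison has 98–100%. Because this is a primary outcome, the rule should be corrected before the data are analysed.

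**What to change.** Make the group coefficient in y = β0 + β1·group + β2·pretest the primary knowledge test at each planned time point. Report it with a confidence interval and state whether the test is one- or two-sided. By step 1 of the working, the same coefficient answers the question about gain, so no second test is needed for that.

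If the interaction is to be kept, centre the pretest at the overall mean of all teachers, so that β1 is the effect at the average pretest. Report β3 with its interval as exploratory effect modification, and remove it from the conditions for concluding that TAPES improves knowledge. Say in the Power Analysis section that the power figure refers to the adjusted group difference.

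The cost is a few sentences of analysis-plan text. No new data, visits or teachers are needed.
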